1.3 RATIONALE FOR PERFORMING THE PROGRAM

The Effisayil-1 trial demonstrated that treatment of GPP flares with spesolimab was associated with rapid pustular and skin clearance, as well as improvements in systemic symptoms and quality of life, with a favourable benefit–risk profile.

This EAP will provide access to the investigational product spesolimab to patients suffering from this serious and potentially life-threatening condition without alternative satisfactory treatment options and not able to be enrolled in a clinical trial.

1.4 BENEFIT - RISK ASSESSMENT/ MEDICAL NEEDS STATEMENT

Spesolimab is an anti-IL-36R antibody with high clinical activity to block IL-36R signaling as shown in patients with GPP, a severe inflammatory skin disease driven by uncontrolled IL-36 activity. The results from the pivotal phase II Effisayil-1 trial suggest that treatment of flare in patients with GPP with spesolimab is associated with rapid and sustained pustular and skin clearance. Improvement in systemic markers supports the beneficial effect of spesolimab on both skin and systemic components of the disease. The overall treatment effect was sustained over time and correlated with improvement in PROs (e.g. pain, fatigue) and quality-of-life measures.

No other IL-36 receptor antagonist is currently approved to provide information on identified risks in molecules of this class.

The risks shown in the table below ([Table 1.4: 1](#)) are derived from general safety considerations of immunomodulatory drugs in clinical development and data generated for spesolimab to date.

Table 1.4: 1

Risks associated with spesolimab administration

Risks of clinical relevance for this program	Summary of data, rationale for the risk	Mitigation strategy
Drug-induced liver injury (DILI)	Although rare, a potential for drug-induced liver injury (DILI) is under constant surveillance by sponsors and regulators. Therefore, DILI is considered as a standard risk in all BI development programs.	Patients with hepatic impairment will be excluded from the program. In case of suspicion of hepatic injury during the program (refer to Section 5.2.4.1.4) patients need to be followed according to a detailed checklist to ensure adequate follow-up and patient safety. Hepatic injury is defined as an AESI.
Systemic hypersensitivity reaction	After administration of any biologic agent or protein, there is a possibility of occurrence of immediate (such as anaphylaxis) or delayed (such as drug reaction with eosinophilia and systemic symptoms) adverse immune reactions.	Patients with a history of allergy/hypersensitivity to spesolimab or its excipients are excluded from the program. In case of systemic hypersensitivity reactions including anaphylactic reaction emerging during or after administration of spesolimab, the investigator should consider, in accordance with severity of the reaction and local standard of care, interruption of therapy and treatment of the condition. Systemic hypersensitivity reaction is defined as an AESI. It is subject to close monitoring and investigators are requested to assess these conditions using the criteria discussed in the statement paper from Sampson et al. [R11-4890].

Table 1.4: 1

Risks associated with spesolimab administration (cont.)

Risks of clinical relevance for this trial	Summary of data, rationale for the risk	Mitigation strategy
Infections	
Inhibition of the immune response with an immune-modulating biologic may increase the risk of infections.
 
In clinical trials with spesolimab, a higher proportion of patients with mild to moderate infections was seen in the spesolimab treatment group than in the placebo treatment group.
 
Nevertheless, there was no indication of an increased frequency of patients with severe, serious, and opportunistic infections in association with spesolimab treatment.
 
A recent characterisation of individuals with homozygous IL36R KO mutations revealed that normal immune function was broadly preserved, suggesting that IL36 signalling pathway inhibition may not substantially compromise host defenses [R17-3632].
	
Patients with any relevant chronic or acute infections including HIV, viral hepatitis or active tuberculosis are excluded from the trial. Treatment of infections should be initiated promptly according to standard of care.
 
Severe infections and opportunistic infections are considered AESI for this program. These conditions and serious infections are subject to close monitoring.

Table 1.4: 1

Risks associated with spesolimab administration (cont.)

Risks of clinical relevance for this trial	Summary of data, rationale for the risk	Mitigation strategy
Malignancies	
Inhibition of the immune response with an immunomodulatory drug may potentially impair immune defences and thus theoretically decrease immune defence against malignancies.
 
A recent characterisation of individuals with homozygous IL36R KO mutations revealed that normal immune function was broadly preserved, suggesting that IL36 signalling pathway inhibition does not compromise host defences [R17-3632].
	
Patients with a recent (within 5 years) history of malignancy will be excluded from participation in this program except appropriately treated basal or squamous cell carcinoma of the skin or in situ carcinoma of uterine cervix.
 
In case of occurrence of malignant neoplasm, other than appropriately treated basal cell carcinoma or squamous cell carcinoma of the skin or in situ carcinoma of uterine cervix, the investigator should discontinue treatment with spesolimab.
 
Diagnostics and treatment will be initiated according to local standard of care.
 
Malignancies always represent SAEs and are subject to close monitoring.

Peripheral Neuropathy	
Three cases reported by the investigator as Guillain-Barré syndrome (GBS) were received in ongoing clinical trials with spesolimab. A panel of independent neurologists and experts in the study of neuropathies assessed the 3 cases. Only 1 met level 4 diagnostic certainty for the diagnosis of GBS (lowest level on Brighton scale of 1 to 4). In that case, there was a coincident infection with SARS-CoV-2. The other 2 cases were assessed as not GBS. Observed cases
	
Timely detection, evaluation, and follow-up of suspected peripheral neuropathies to ensure patients' safety.
 
Use of dedicated questions to elicit neurologic history during screening and exclusion criteria to avoid selection of patients with acute demyelinating neuropathy.
 
Targeted Follow up questions to gather detailed information in case of any event during trial to ensure proper decision making.

Table 1.4: 1

Risks associated with spesolimab administration (cont.)

Risks of clinical relevance for this trial	Summary of data, rationale for the risk	Mitigation strategy
	showed a heterogenous pattern. As per assessment by the panel of external neurologists the nonspecific symptoms and findings in all three cases may best be referred to as peripheral neuropathy.	Trial treatment discontinuation criteria as well as criteria for trial treatment restart are implemented for relevant cases.

Other risks related to program-specific procedures include blood sampling and [REDACTED] of study medication, which can cause local bruising, inflammation, nerve damage and pain.

Based on the findings in nonclinical studies conducted to date and in accordance with international regulatory guidelines, the inclusion of Women of Child Bearing Potential (WOCBP) in this program is justified. To minimize the risk of unintentional exposure of an embryo or foetus to the investigational drug, WOCBP must agree to the requirements for the pregnancy testing and contraceptive methods described in the protocol.

Benefit-risk assessment in context of COVID-19 pandemic for patients receiving the investigational product spesolimab

A thorough assessment based on the data available as of 29 April 2021 has been conducted to evaluate whether spesolimab may pose a higher risk associated with COVID-19 infection. Additionally, the general risk of COVID-19 infection in context of the trial population's underlying disease and common co-morbidities was assessed. The key aspects of the assessment are summarized below.

Spesolimab is an immune-modulating humanized monoclonal antibody that blocks the human IL-36 receptor and thereby the pro-inflammatory IL-36 pathway. As reflected in [table 1.4:1](#) above and the patient informed consent form, similar to other immune modulating biological treatments, spesolimab may potentially increase the risk of infections. Therefore, risk mitigation measures, such as exclusion of patients with increased risk of infections, close monitoring of adverse events, as well as guidance on treatment and handling of acute infections occurring during the trial have been included within this EAP protocol.

As with any other acute infection, a suspected or diagnosed COVID-19 infection should be treated according to the standard of care and interruption of study medication should be considered.

Currently, information about the immune response in patients with COVID-19 is sparse and inconclusive. There are some reports suggesting high levels of pro-inflammatory cytokines in severe cases, with much of the morbidity associated with coronavirus infection potentially related to immune activation and inflammation. To date, there is no reliable evidence

suggesting a link between SARS-CoV-2 infections and the IL-36 pathway targeted by spesolimab. Considering the current knowledge of COVID-19 and the implemented risk mitigation measures addressing the potential risk of infections, patients receiving the investigational product spesolimab are not believed to be at higher risk of COVID-19 owing to their background or concomitant diseases. Protocol-defined procedures do not impose undue risk to program participants.

The benefit–risk assessment of spesolimab remains favourable in the context of the COVID-19 pandemic. Patients receiving the investigational product spesolimab are expected to benefit from treatment and interruption of treatment may worsen their disease. Published guidance for the use of biologics during the COVID-19 pandemic recommends to continue treatment with biologics (e.g. NICE COVID-19 rapid guideline: severe asthma ([R20-2257](#)), American College of Allergy, Asthma & Immunology ([R20-2258](#)), and National Psoriasis Foundation ([R20-2256](#))). In line with this guidance no systematic testing for SARS-CoV-2 is required to be performed in this program. However, the treating physician may choose to perform the testing as per his or her discretion if useful based on individual medical consideration and in the case of suspected COVID-19 infection.

To address potential risks associated with operational aspects related to the participation in this EAP in context of COVID-19 pandemic, the following risk mitigation measures are to be considered based on local requirements and development of pandemic.

Every subject or patient will be assessed thoroughly, and individual benefit–risk assessments are made prior to program enrolment and during the program by the treating physician with respect to SARS-CoV-2 infection. As with any other acute infection, a suspected or diagnosed COVID-19 infection should be treated according to the standard of care and interruption of spesolimab should be considered. In case of a confirmed infection, spesolimab should not be administered and appropriate measures for monitoring, treatment and quarantine will be implemented. The treating physicians will take the totality of information related to each single patient and the local COVID-19 situation into consideration when performing the individual benefit–risk assessment on a case-by-case basis. The patient may be eligible for spesolimab treatment following recovery from a SARS-CoV-2 infection if the patient is expected to derive clinical benefit, as agreed between the treating physician and sponsor.

Considering that GPP flares constitute a serious and potentially life-threatening condition, and the fact that currently used treatments have limited evidence supporting efficacy and safety, the potential benefit of spesolimab for the treatment of flares in adult patients with GPP is considered to outweigh the potential risks, therefore justifying providing expanded access to patients suffering from this condition.

2. PROGRAM OBJECTIVES AND ENDPOINTS

2.1 MAIN OBJECTIVES, PRIMARY AND SECONDARY ENDPOINTS

2.1.1 Main objectives

The aim of this program is to provide early access to the investigational drug spesolimab for patients with GPP presenting with a flare. A secondary aim of this program is to collect additional data on the safety and tolerability of spesolimab.

2.1.2 Primary endpoint

- Occurrence of Treatment Emergent Adverse Events (AEs)

2.1.3 Secondary endpoints

- Occurrence of Treatment Emergent Serious Adverse Events (SAEs)
- Occurrence of Treatment Emergent Adverse Events of Special Interest (AESIs)

3. DESCRIPTION OF DESIGN AND PROGRAM POPULATION

3.1 OVERALL PROGRAM DESIGN AND PLAN

This is an open-label, multi-centre, single-arm trial, designed to provide early access to spesolimab, for patients with GPP presenting with a flare and for whom no satisfactory authorised alternative therapy exists and who are unable to participate in a clinical trial, as assessed by the treating physician.

After signing informed consent and if all eligibility criteria are met, patients will receive a [REDACTED] spesolimab. If deemed necessary by the treating physician (i.e. if the flare symptoms persist), a [REDACTED] spesolimab may be administered [REDACTED] after the initial [REDACTED].

If [REDACTED] is administered, then patients will visit the treating physician approximately at week [REDACTED], week [REDACTED] and week [REDACTED]. If a [REDACTED] may be given, then the dates that patients will visit the treating physician is changed to approximately at [REDACTED] [REDACTED] after initial dose of spesolimab. Please refer to section [6.1](#) for details on the program visit procedures. Patient's participation in the program will end after conclusion of the [REDACTED]-week follow-up period after the last [REDACTED] / drug administration.

If a patient experiences a new GPP flare (following the resolution of a previous flare with spesolimab treatment) after the [REDACTED]-week follow-up period the patient may re-enter in the program and be treated again with spesolimab, providing eligibility criteria are still met and the overall program is still running. The same dosing and follow-up requirements apply as for the previous flare.

In the situation that a patient experiences a new GPP flare within the [REDACTED]-week follow-up period and the physician wishes to treat this new flare with spesolimab, eligibility needs to be assessed and agreed upon with the BI clinical team.

The enrolment of patients for the program will stop at the time spesolimab becomes commercially available or 6 months after marketing authorization for treatment of GPP in China (whichever is earlier). The overall program will close when the last patient completes the follow up period after the last [REDACTED] of spesolimab or if any other reason listed in section [3.2.4.3](#) is met.

Below is suggested flow chart for patient visit.

Flow Chart

Trial Period	Screening	Treatment		Follow-up Period		
Visit	V1 ¹	V2 ¹	V3 ²	V4	V5	V6/EoS ³
Week [REDACTED]) ²						
Week [REDACTED]) ²						
Window			±1d	±1d	±7d	±7d
Informed consent	X					
Demographics	X					
Medical history	X					

Proprietary confidential information © 2022 Boehringer Ingelheim International GmbH or one or more of its affiliated companies

Trial Period	Screening		Treatment		Follow-up Period	
	V1 ¹	V2 ¹	V3 ²	V4	V5	V6/EoS ³
Visit						
Week [REDACTED] ²						
Week [REDACTED] ²						
Window			±1d	±1d	±7d	±7d
Baseline condition	X					
Physical examination	X	X	(X) ⁵	(X) ⁵	(X) ⁵	(X) ⁵
Vital signs	X	X	(X) ⁵	(X) ⁵	(X) ⁵	(X) ⁵
Pregnancy test ⁴	X					
Infection testing ⁶	X					
Safety laboratory tests (Local lab) ⁷	X		(X) ⁵	(X) ⁵	(X) ⁵	(X) ⁵
Nucleic acid testing	X					
COVID-19 symptoms		(X)	(X)	(X)	(X)	(X)
Review of in-/exclusion criteria	X	X				
IRT transaction	X	X	X			
Dispense/administration study drug		X	X			
Adverse events	X	X	X	X	X	X
Concomitant therapy	X	X	X	X	X	X
[REDACTED]						
Study Completion						X

Abbreviations: EoS: end of study; IRT: Interactive Response Technology; V: Visit.

- 1: Visit 1 and Visit 2 can be on the same day. If V1 and V2 is performed on the same day, the procedures do not need to be repeated.
- 2: V3 is an additional visit. There's a possibility that patient will receive [REDACTED] of spesolimab at V3 [REDACTED] if his flare symptoms persist after the [REDACTED] dose. If in that case, the visit schedule will be changed to approximately at [REDACTED] after initial dose of spesolimab.
- 3: Should a patient prematurely discontinue from the treatment; every effort should be made to keep the patient in the trial and complete all of the remaining study visits. If a patient is not willing to follow the whole visit schedule, the EOS Visit (Visit 6) should be conducted at [REDACTED] weeks after the last spesolimab administration at a minimum. If patients refuse to return to the study site, early EoS visit should be completed at the timing of prematurely discontinuation and then at least safety information should be collected by phone at [REDACTED] weeks after the last spesolimab administration.
- 4: Only applicable for women of childbearing potential.
- 5: Physical examination, vital signs and safety laboratory test shown with parentheses "(X)" are optional and will be performed according to standard clinical practice and when deemed appropriate by the investigator.
- 6: Infection testing includes tuberculosis, viral hepatitis tests (at least to include anti-hepatitis B core antibody, hepatitis B surface antigen, hepatitis C virus antibody) and HIV assessments.
- 7: Safety laboratory tests at screening visit (Visit 1) include liver function test (at least to include AST/GOT, ALT/GPT, alkaline phosphatase, and total bilirubin), haematology test (at least to include complete blood count with differential).

[REDACTED]

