5.2.4.1.4 Adverse events of special interest

The term adverse events of special interest (AESI) relates to any specific AE that has been identified at the project level as being of particular concern for prospective safety monitoring and safety assessment within this program, e.g. the potential for AEs based on knowledge from other compounds in the same class. AESIs need to be reported to the sponsor’s Pharmacovigilance Department within the same timeframe that applies to SAEs, please see section [5.2.4.2.2](#).

The following are considered as AESIs:

Potential Severe DILI

A potential severe DILI that requires follow-up is defined by the following alterations of hepatic laboratory parameters:

- an elevation of AST (aspartate transaminase) and/or ALT (alanine aminotransferase) ≥ 3 fold ULN combined with an elevation of total bilirubin ≥ 2 fold ULN measured in the same blood draw sample, or in samples drawn within 30 days of each other, or
- ALT, and/or AST elevations ≥ 10 fold ULN.

These lab findings constitute a hepatic injury alert and the patients showing these lab abnormalities need to be followed up according to the “DILI checklist” provided in the ISF. In case of clinical symptoms of hepatic injury (icterus, unexplained encephalopathy, unexplained coagulopathy, right upper quadrant abdominal pain, etc.) without lab results

Proprietary confidential information © 2022 Boehringer Ingelheim International GmbH or one or more of its affiliated companies

(ALT, AST, alkaline phosphatase, total bilirubin) available, the investigator should make sure these parameters are analysed. Should the results meet the criteria of hepatic injury alert, the procedures described in the DILI checklist should be followed.

Systemic hypersensitivity reactions including [REDACTED] reactions and anaphylactic reaction
Any suspicion of severe systemic hypersensitivity including [REDACTED] reactions and any anaphylactic reaction should be defined and assessed using the criteria discussed in the statement paper from Sampson et al. (Section [4.2.1.1](#) and Appendix [10.1, R11-4890](#)).

Severe infections (according to RCTC grading in the ISF)

Opportunistic and mycobacterium tuberculosis infections

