7. PLANNED ANALYSIS

For End-Of-Text (EoT) tables, the set of summary statistics is N / Mean / SD / Min / Q1 / Median / Q3 / Max.

For tables that are provided for endpoints with some extreme data, median, quartiles and percentiles should be preferred to mean, standard deviation, minimum and maximum.

Tabulations of frequencies for categorical data will include all possible categories and will display the number of observations in a category as well as the percentage (%) relative to the respective treatment group (unless otherwise specified, all patients in the respective patient set whether they have non-missing values or not).

The precision for percentages should be one decimal point, unless the denominator is smaller than 100 (in all treatment columns), in which case percentages are given in integer numbers. The category “missing” will be displayed only if there are actually missing values.

Disposition of the patient population participating in the trial will be summarised by the presentation of the frequency of patients enrolled, enrolled but not treated, enrolled and treated, who completed participation in the trial, and who were prematurely discontinued from trial, by reason. The iPDS, baseline conditions/medical history, demographic/baseline characteristics, concomitant medications, concomitant non-drug therapies, exposure will be presented based on TS for the entire trial duration. In addition, the number of flares will also be summarized based on TS.

For safety data, per patient analysis based on patient will be used for the analysis, whose denominator will be the number of patients or time at risk per patient for all applicable periods.

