7.8 SAFETY ANALYSIS

All safety analyses will be performed following BI standards. No hypothesis testing is planned.

For all flare treatment period (all flares for a patient combined) based on TS, the AE data and possibly clinically significant laboratory abnormalities will be analysed under OR (as defined in [Section 6.6](#))

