Table 7.8.1: 1 Project MedDRA search criteria for User Defined Adverse Event Categories

User-defined AE category		
	Label	Description
Infections (serious/severe, opportunistic)	Infections ALL	Combined search strategy based on the individual UDAECs described below; the UDAEC “severe infections (investigator-defined) will be disregarded for this search
	Opportunistic infections	Narrow SMQ “Opportunistic infections”
	Tuberculosis infections	BIcMQ “Infections”: Narrow sub-search 8.2 “Tuberculosis related terms”
	Serious infections	all serious events in SOC “Infections and infestations”
	Severe infections	all events in SOC “Infections and infestations” of at least severe RCTC grade, by HLGT
Hypersensitivity	Hypersensitivity ALL	Combined search strategy based on the individual UDAECs described below
	Anaphylactic reaction	Narrow SMQ “Anaphylactic reaction”
	Angioedema	Narrow SMQ “Angioedema”
	Hypersensitivity	Narrow SMQ “Hypersensitivity”
	DRESS, algorithmic	
Based on broad SMQ “Drug reaction with eosinophilia and systemic symptoms” (SMQ code 20000225), defined using algorithm as follows:
 
A or (B and C and D) or (B and C and E) or (B and D and E)
 
where the categories A, B, C, D and E are defined categorisations of the PTs of the SMQ. For PTs of category A only narrow scope is used, for all other categories broad scope is used.
 
For identification of potential DRESS through the combination of adverse event occurrences within each of the categories B, C, D and E, adverse event start and end dates will be used. For the latter, potential DRESS is then identified if, within a 7-day period after occurrence of a relevant contributing event (assessed on each day between start and end date [inclusive] of the initiating event), there is at least one adverse event reported (based on start date only) from each of the other applicable categories within a specific combination of categories as described above (in parentheses).
 
If the end date is missing, the event is considered to be ongoing, and end date will be the last day of the applicable treatment period

	DRESS, narrow	Narrow SMQ “Drug reaction with eosinophilia and systemic symptoms”, any event within category A only

Malignancies	Malignant tumours	Narrow Sub-SMQ "Malignant tumours" Narrow Sub-SMQ "Haematological malignant tumours" Narrow Sub-SMQ "Non-Haematological malignant tumours"
	Malignant skin tumours	Broad Sub-SMQ "Skin malignant tumours"

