7.8.2 Laboratory data

Clinically relevant findings in laboratory data will be reported as baseline conditions (at screening) or as AEs (during the trial) if judged clinically relevant by investigator, and will be analyzed as such.

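### Potential severe DILI is defined only by liver tests that are not routine after dosing, so a zero or low hepatic count cannot be interpreted without the number of patients tested, and it is the one listed AESI with no MedDRA search

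*Protocol*

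**What the plan says.** **Endpoint and case definition.** Protocol 2.1.3 lists "Occurrence of Treatment Emergent Adverse Events of Special Interest (AESIs") as a secondary endpoint. For the liver, Protocol 5.2.4.1.4 states: "A potential severe DILI that requires follow-up is defined by the following alterations of hepatic laboratory parameters". The criteria are AST and/or ALT at least 3 times ULN with bilirubin at least 2 times ULN (same draw or within 30 days), or AST and/or ALT at least 10 times ULN. It adds: "These lab findings constitute a hepatic injury alert".

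**When liver tests are taken.** Screening tests are required (Protocol 3.1 flow chart, 5.2.3 and 6.1.1). From V3 to V6, footnote 5 of the flow chart says that safety laboratory tests "are optional and will be performed according to standard clinical practice and when deemed appropriate by the investigator"; Protocol 5.2.3 likewise leaves further testing to the physician. Two triggers exist: hepatic symptoms without results (5.2.4.1.4) and suspected delayed hypersensitivity (4.2.1.1).

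**Denominator.** SAP 6.3 uses the treated set for everything except disposition. SAP 7 describes a per-patient safety analysis "whose denominator will be the number of patients or time at risk per patient for all applicable periods". Under SAP 7.8.1, a patient without the event is censored at death, last contact or the end of the treatment period.

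**Source of cases.** SAP 7.8.1 takes AESIs from the investigator's eCRF entry and reports MedDRA searches separately in the table titled "Project MedDRA search criteria for User Defined Adverse Event Categories".

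**Laboratory data.** SAP 7.8 says that "possibly clinically significant laboratory abnormalities will be analysed under OR", the approach set out in SAP 6.6. SAP 7.8.2 says: "Clinically relevant findings in laboratory data will be reported as baseline conditions (at screening) or as AEs (during the trial"), if the investigator judges them relevant.

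**The concern.** Without a liver test there can be no case under this definition, yet patients never tested after dosing count as event-free for their whole follow-up. A zero or low hepatic count would therefore mix two situations: patients tested and found normal, and patients without symptoms who were not tested. No planned output shows how many belong to each. Collecting safety data is a stated secondary aim of the program and hepatic injury is the first risk in Protocol Table 1.4: 1, so readers will interpret that count.

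The second route to safety topics, the MedDRA searches, leaves out the liver. A reported hepatic event that was not flagged as an AESI would appear only under its own preferred term. The SAP is also unclear on whether laboratory abnormalities are analysed in any way other than as adverse events.

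**Working it through.** **1. No planned figure to reproduce.** The documents give no sample size, expected DILI rate or expected testing frequency. The one related figure is consistent: 16 weeks in Protocol 7.1.1 is 16 × 7 = 112 days, as in SAP Table 6.1: 1.

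**2. Time added by an untested patient.** For a single dose with full follow-up, (112 + 1)/365.25 = 0.309 patient-years enter the denominator, and a case can enter the numerator only if a test is done.

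**3. Direction.** Let s be the share of true cases with symptoms, assumed all tested, and c the chance that an asymptomatic case is tested while abnormal. Then, approximately,

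observed rate / true rate = s + (1 − s) × c.

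This cannot exceed 1. It equals 1 only if every true case has symptoms (s = 1) or every asymptomatic case is caught (c = 1). The documents give neither s nor c, so the values below are assumptions.

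| s | c | observed / true |
|---|---|---|
| 0 | 0.25 | 0.25 |
| 0.25 | 0.25 | 0.25 + 0.75 × 0.25 = 0.44 |
| 0.5 | 0.5 | 0.5 + 0.5 × 0.5 = 0.75 |
| 1 | any | 1.00 |
| any | 1 | 1.00 |

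**4. Effect on a reported rate.** Assume 100 single-dose patients and 2 true cases, with full time counted for all. The true rate is about 100 × 2/(100 × 0.3094) = 6.46 per 100 patient-years. The expected reported rate is 6.46 × 0.75 = 4.85, 6.46 × 0.4375 = 2.83 or 6.46 × 0.25 = 1.62 in the third, second and first rows.

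**5. Effect on a zero count.** Assume 50 single-dose patients and no recorded case. The one-sided 95% upper bound is 100 × (−ln 0.05)/(50 × 0.3094) = 19.4 per 100 patient-years if every case would have been detected. Dividing the unrounded bound, 19.37, by the same ratios gives 19.37/0.75 = 25.8, 19.37/0.4375 = 44.3 and 19.37/0.25 = 77.5. The same zero supports quite different statements.

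**6. The five listed AESIs against SAP Table 7.8.1: 1.**

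| AESI in SAP 7.8.1 | Search in the table |
|---|---|
| Potential severe DILI | none |
| Systemic hypersensitivity | yes |
| Severe infections | yes |
| Opportunistic and tuberculosis infections | yes |
| Peripheral neuropathy | yes |

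The table also covers malignancies, 3-point MACE and torsades de pointes, none of which is a listed AESI.

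**7. Laboratory wording.** SAP 6.6 and 7.8 announce an analysis of laboratory abnormalities; SAP 7.8.2 describes none beyond baseline conditions and adverse events. No section defines the abnormalities.

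**The case against.** The strongest reply is that testing is not absent but prompted by suspicion. Hepatic symptoms without results call for liver parameters, suspected delayed hypersensitivity calls for a panel with liver enzymes, adverse events are asked about at every visit, and re-entry for a new flare repeats the screening tests. This stands. It confines the problem mainly to asymptomatic elevations, and a reader who inferred that nobody looked, or that the event could not be detected, would go too far.

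Three other inferences are tempting and not supported:

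- *That the rate is understated by the inverse of the share tested.* This requires testing to be unrelated to the event. The Protocol ties testing to clinical judgement and symptoms, and having one test is not the same as being tested while abnormal.
- *That the thresholds are never applied.* Investigators apply them: meeting them is a hepatic injury alert with checklist follow-up (Protocol 5.2.4.1.4), and AESIs go to the sponsor within 24 hours (5.2.4.2.2). What the SAP lacks is a programmed check by the sponsor, which is possible only if post-dose values are in the database. The documents do not clearly show that they are.
- *That a rate in tested patients is the corrected rate.* These patients are partly selected by indication, so their rate would tend to overstate incidence in all treated patients.

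It is also fair to say that a MedDRA search cannot find an elevation that was never measured, that reported hepatic events are already tabulated by system organ class and preferred term, that the endpoint is AESIs as a whole, and that the analysis is descriptive in a program whose main aim is access. These points limit the weight of the concern. They do not tell a reader of the results how many patients were tested.

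**Conclusion.** The concern holds in a limited form. Potential severe DILI depends wholly on laboratory values that are not routinely obtained after dosing, while every treated patient contributes time at risk. Asymptomatic elevations can be missed, and any resulting detection bias is downward. Its size is unknown; the ratios of 0.25 to 1.00 rest on assumed values of s and c and only show how wide the possibilities are. No hypothesis test is affected. What is affected is how much reassurance a zero or low hepatic count can give.

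The missing hepatic search is a separate and smaller gap: it leaves reported but unflagged hepatic events ungrouped. The laboratory wording in SAP 6.6 and 7.8 needs reconciling with 7.8.2. All three matters are cheap to settle and worth settling before the analysis.

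**What to change.** No additional blood tests and no change to patient care are involved.

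1. In SAP 7.8.1, report the number and share of treated patients with at least one post-dose ALT, AST or bilirubin result beside the treated-set DILI result, and state that a zero or low count is to be read against it. Any rate in tested patients should be supplementary and labelled as selected by indication.
2. Add a hepatic row to Table 7.8.1: 1, for example the narrow SMQ for drug-related hepatic disorders including liver investigations. Note that it recovers events reported but not flagged, not cases never tested.
3. Reconcile SAP 6.6 and 7.8 with 7.8.2: either define the laboratory abnormalities and their analysis, or remove the reference. Apply the Protocol 5.2.4.1.4 thresholds by program only if post-dose values are captured in the database.

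The cost is SAP wording and possibly one yes/no eCRF item on whether a post-dose liver test was done. The statement about hepatic safety may become less reassuring. Capturing numeric post-dose values, if they are not already collected, would cost more and is not needed for items 1 and 2.
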